8.3 Demographic and Baseline Characteristics

Descriptive statistics will be summarized for the subjects in the Safety Analysis Population and for the subjects in the Per Protocol population (both in total and by treatment):

- Age at consent (in years);
- Sex;
- Child's bearing potential if Sex is Female;
- Hispanic/Latino;
- Race;
- Height (cm);
- Weight (kg);
- BMI (kg/m²).

8.4 Operative details

Operative details will be summarized for the subjects in the Safety Analysis Population and for the subjects in the Per Protocol population (both in total and by treatment group):

- Primary diagnosis;
- Occurrence of Intraoperative complication(s) (Y/N);
- ASA Risk;
- Surgical time (Duration) (min);
- Anesthesia time (Duration) (min);

- Femoral broaching time (Duration) (min);
- Surgical approach;
- Use of Hana table
- Use of standard table if Hana table was not used
- Use of intraoperative fluoroscopy to position the cup
- Starting broach size;
- Ending broach size;
- Skipped any broach size (Y/N); If any broach sizes were skipped then provide a listing of which sizes were skipped;
- Use of KINCISE (Yes/No);
- Listing of steps taken when KINCISE was used;
- Use of a mallet;
- Listing of steps taken when mallet was used;
- Use of wires/cables (Y/N);
- Use of screws (Y/N);
- Listing of additional details when screws were used;
- Cup need to be repositioned after the initial impaction (Y/N);
- Use of KINCISE when cup was needed to be repositioned after the initial impaction (Y/N);
- Established preoperative target(s) for inclination during the surgery was changed (Y/N);
- New target in degrees if established preoperative target(s) for inclination during the surgery was changed;
- Established preoperative target(s) for version during the surgery was changed (Y/N);
- New target in degrees if established preoperative target(s) for version during the surgery was changed;
- Acetabular bone graft;
- Acetabular bone class;

- Acetabular osteophytes removed (Y/N);
- Femoral bone graft;
- Femoral bone class proximal;
- Femoral bone class distal;
- Femoral DORR class;
- Femoral stem component present (Y/N);
- Femoral head component present (Y/N);
- Acetabular shell (cup) component present (Y/N);
- Acebabular liner (insert) component present (Y/N);
- EMG data uploaded to Athos (Y/N).

8.5 Post-operative details

Post-operative details will be summarized for the subjects in the Safety Analysis Population and for the subjects in the Per Protocol population (both in total and by treatment group):

- Subject taking any narcotic pain medication to manage study hip pain (Y/N);
- Hospital stay less than 24 hours (Y/N);
- Length of hospital stay in days (date of discharge minus date of surgery);
- Location of discharge;
- Narcotics prescribed for pain management (Y/N).

8.6 Device Deficiencies and Protocol Deviations

Listings of device deficiencies and protocol deviations will be provided.

8.7 Primary Endpoint and Associated Hypotheses

The primary endpoint analysis is to demonstrate that femoral broaching time (in minutes)

with KINCISE is non-inferior to femoral broaching time with manual instruments (not using KINCISE) under a non-inferiority margin of 1.25 minutes.

Hypotheses for this non-inferiority analysis are as follows:

- Null Hypothesis: $H_0: \mu_I \ge \mu_C + 1.25$
- Alternative Hypothesis: H_A : $\mu_I < \mu_C + 1.25$

where μ_I and μ_C are mean femoral broaching times with and without KINCISE, respectively, and 1.25 is the NI margin. The null hypothesis will be rejected and non-inferiority will be concluded if the 1-sided upper 95% confidence limit for the $\mu_I - \mu_C$ difference (based upon a 2-sample t-test) is less than 1.25. The study will be deemed to be successful if this analysis demonstrates non-inferiority of femoral broaching time.

If non-inferiority is successfully demonstrated, then a test for superiority will be conducted to assess if femoral broaching time with KINCISE is less than femoral broaching time without KINCISE with statistical significance (1-tailed t-test with 5% alpha).

The primary endpoint analysis and all associated hypotheses will be conducted on the Per Protocol Analysis Set.

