7.1 Pre-operative Evaluation (-180 Days to Date of Surgery)

The following data will be collected from the pre-operative evaluation:

- Informed Consent
- Study Visit (CRF detailing type of visit and subject status)
- Eligibility
- Randomization
- Demographics
- Targeted Medical History (self-reported by subject or within clinic notes)
- Height and Weight (Collected on Vital Signs CRF)
- Narcotic Drug Use (patient reported)
- Preoperative Hip Evaluation (HE1)
- Harris Hip Score
- Radiographs (AP Hip (unilateral), AP Pelvis (bilateral), and Lateral)
- EQ-5D-5L
- Preoperative Planning Details (planned inclination and anteversion, planned cup & stem size)
- **OPTIONAL:** Preoperative templates (used for planning cup position, cup & stem size) Note: The Sponsor is requesting submission of preoperative templates, to be included with the preoperative radiographs, if the surgeon/site templates per their standard of care. Templating is not a requirement for participation in the study
- Protocol Deviation Form (if needed)

Confidential Version Date: 040CT2021

DePuy Synthes Protocol DSJ_2019_03 / Version 2.0 / TV-eFRM-02920 End of Study (Withdrawal) Case Report Form (if needed)

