The following analysis sets are defined:

- Enrolled The Enrolled population set will consist of all subjects who sign the informed consent document.
- Safety The Safety population set will consist of all subjects in the Enrolled population set for whom treatment was attempted, according to the actual treatment received.
- Per Protocol The Per Protocol population set will consist of all subjects in the Enrolled population set who successfully received the planned treatment, who met all inclusion/exclusion criteria, who were seen at least once at a post-operative visit, and who did not have any protocol deviations which were prospectively determined to potentially have influence on the scientific validity of the data (such as inclusion/exclusion criteria).

7 Sample Size Justification

Primary endpoint Non-Inferiority (NI) analysis: Based upon input from key opinion leaders (KOLs) and data from other studies, typical femoral broaching time with manual instruments is anticipated to have a range of 5 to 15 minutes, which implies a standard deviation of approximately 2.5 minutes (1/4 of the range). Moreover, KOLs suggest that a difference of 10 minutes in femoral broaching time (increase for a single patient) is clinically meaningful. The non-inferiority margin of 1.25 minutes was established because it Page 8 of 29

is ½ of the anticipated standard deviation and is much less than a clinically meaningful difference. Under a 1-sided test with 5% alpha, a sample size of N=88 per group would be sufficient to demonstrate non-inferiority with 95% power. A sample of size N=200 per group (N=400 total) was chosen as feasible by the sponsor and desirable for providing further data for both KINCISE and Anterior Advantage; this sample size would provide more than 99% power to demonstrate non-inferiority for the primary endpoint analysis.

Primary endpoint supplemental superiority analysis: It is not known if there will be a true difference in means between groups. However, if there is a true difference of 1 minute between group means (lower time favoring KINCISE), and assuming an SD as stated above (2.5 minutes), then a sample of N=200 per group (N=400 total) would provide approximately 99% power to demonstrate superiority.

Secondary endpoint analyses:

• Non-inferiority of skin-to-skin OR time

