Based upon input from KOLs and data from other studies, skin-to-skin OR time is anticipated to have a typical range from 60 to 90 minutes, which implies a standard deviation of approximately 7.5 minutes (1/4 of the range). The non-inferiority margin of 3.75 minutes was established because it is ½ of the anticipated standard deviation and is much less than the 10 minute clinically meaningful difference in femoral broaching time (a subset of skin-to-skin OR time). Under a 1-sided test with 5% alpha, a sample size of N=200 per group would be sufficient to demonstrate non-inferiority with greater than 99% power.

• Non-inferiority of optimal acetabular cup abduction

The percent of subjects within +/- 10 degrees of planned cup abduction for an anterior approach (AA) is anticipated to be between 90% and 95% (based on studies presented by Hamilton¹ and Rathod², respectively). These are a clinical improvement from percentages exhibited with a posterior approach (PA), which were 79% and 86% in [1] and [2], respectively. A NI margin of 10% was chosen because it is less than the improvement from PA to AA observed by Hamilton¹ and

Rathod². With this margin and a 1-sided test with 5% alpha, a sample size of N=200 per group would be sufficient to demonstrate non-inferiority with approximately 95% power.

• Non-inferiority of optimal acetabular cup abduction

The percent of subjects within +/- 10 degrees of planned cup version for an anterior approach (AA) is anticipated to be between 91% and 92% (based on studies by Rathod² and Hamilton¹, respectively). These are a clinical improvement from percentages exhibited with a posterior approach (PA), which were 64% and 77% in [1] and [2], respectively. A NI margin of 10% was chosen because it is less than the improvement from PA to AA observed by Hamilton¹ and Rathod². With this margin and a 1-sided test with 5% alpha, a sample size of N=200 per group would be sufficient to demonstrate non-inferiority with approximately 95% power.

In summary, with a sample size of N=400 (200 with KINCISE; 200 without KINCISE), the anticipated overall likelihood of demonstrating the primary endpoint non-inferiority analysis, followed by the three stated secondary endpoint non-inferiority analyses in the specified gate-keeping order, is at least $(99\%)(99\%)(95\%)(95\%) \approx 88\%$.

8 Analyses to be Conducted

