8.8 Secondary Endpoints and Associated Hypotheses

All secondary endpoint analyses and associated hypotheses will be conducted on the Per Protocol Analysis Set.

If the primary endpoint analysis successfully demonstrates non-inferiority of femoral broaching time, regardless of whether the above test of superiority was successful or not, then the following three secondary endpoint analyses will be conducted under a gatekeeping strategy, in this specified order, where testing is performed in sequence and continues until a null hypothesis is not rejected or all hypotheses have been tested, each with a 1-sided alpha of 0.05:

- 8.8.1 Skin-to-skin OR time
 - Skin-to-skin OR time in minutes will be summarized as a continuous variable for both treatments and combined
 - A non-inferiority test of skin-to-skin OR time will be conducted with a noninferiority margin of 3.75 minutes, using a 2-sample t-test:
 - Null Hypothesis: $H_0: \mu_I \ge \mu_C + 3.75$
 - Alternative Hypothesis: H_A : $\mu_I < \mu_C + 3.75$
 - where μ_I and μ_c are mean skin-to-skin OR times with and without KINCISE, respectively. The null hypothesis will be rejected and non-inferiority will be concluded if the 1-sided upper 95% confidence limit for the μ_I μ_c difference (based upon a 2-sample t-test) is less than 3.75
 - The 1-sided upper 95% confidence limit for the difference and the pvalue will be presented.
- 8.8.2 The percent of subjets with acetabular cup abduction angle within +/- 10 degrees of plan
 - The proportion of subjets with acetabular cup abduction angle within +/- 10 degrees of plan will be summarized for both treatments and combined
 - A non-inferiority test of the percent of subjects with acetabular cup abduction angle within +/- 10 degrees of plan under a NI margin of 10% will be conducted:
 - Null Hypothesis: $H_0: P_I \le P_C 10\%$
 - Alternative Hypothesis: $H_A: P_I > P_C 10\%$
 - where P_I and P_c are the percentages of subjects with acetabular cup abduction angle within 10% of plan with and without KINCISE, respectively. The null hypothesis will be rejected and non-inferiority will be concluded if the 1-sided lower 95% confidence limit for the P_I –

 P_{C} difference (based upon a normal approximation method) is greater than -10%

- The 1-sided lower 95% confidence limit for the difference and the pvalue will be presented.
- 8.8.3 The percent of subjects with acetabular cup version angle within +/- 10 degrees of plan

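### Optional precision gain: both operating-time tests are unadjusted, although pre-operative predictors (sex, BMI and, for broaching time, planned stem size) are already collected

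*SAP*

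**What the plan says.** The primary comparison (SAP 8.7; Protocol 10.5.1 and 10.9.3) is a two-sample t-test "under a non-inferiority margin of 1.25 minutes". The criterion is that the one-sided upper 95% limit for the "difference (based upon a 2-sample t-test) is less than 1.25". If it succeeds, superiority follows as a "1-tailed t-test with 5% alpha". OR time (SAP 8.8.1; Protocol 10.5.2 and 10.9.4) is tested with a "margin of 3.75 minutes, using a 2-sample t-test". No covariate or site term appears in any of these tests. SAP 8.13 rules out sensitivity analyses and SAP 8.15 rules out a formal look at site homogeneity, so no adjusted analysis exists elsewhere in the plan.

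The data for adjustment are there. Protocol 7.1 collects "Preoperative Planning Details (planned inclination and anteversion, planned cup & stem size", together with demographics, height and weight. SAP 8.3 summarises sex and BMI. SAP 8.4 lists the starting broach size, any skipped sizes and "Ending broach size" among the operative details.

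SAP 7 says of the range for broaching time, "which implies a standard deviation of approximately 2.5 minutes (1/4 of the range", and of the range for OR time, "which implies a standard deviation of approximately 7.5 minutes (1/4 of the range". SAP 3 describes one sticker set per site in fixed blocks of four.

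**The concern.** In a randomised comparison of means, any baseline variable that predicts the outcome but is left out leaves its share of the variance in the standard error. The confidence limits are then wider than the collected data allow.

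Sex and BMI are plausible predictors of operating time. For broaching time, planned stem size is plausible too. Protocol 4.1 runs the clock from first entry of the box osteotome to seating of the final broach trial, and the sizes listed in SAP 8.4 suggest progression through a sequence. Planned size is a pre-randomisation proxy for where that sequence ends.

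Precision would matter in two situations that the plan leaves open. Both SDs are a quarter of a typical range and may be too small. SAP 7 also says that the true difference is unknown, and its superiority power of about 99% applies only to a gain of 1 minute.

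**Working it through.** **Inputs from SAP 7, 8.7 and 8.8.1.** SD 2.5 min (broaching) and 7.5 min (OR time); margins 1.25 and 3.75 min; one-sided alpha 5%; 200 per arm.

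**Assumed, because the documents are silent.** R-squared of 5% to 30% (share of within-arm variance explained), a true gain of 0.5 min, and a doubled SD.

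**Formulas.** SE = SD × √(1 − R²) × √(2/200), where √(2/200) = 0.1. Distance from estimate to limit = 1.6487 × SE (t, 398 df). Power is from the noncentral t with noncentrality d/SE, where d is the margin (non-inferiority, true difference zero) or the true gain (superiority).

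**1. The plan's own figures reproduce.** The smallest n per arm giving 95% non-inferiority power is 88 (87 by the normal approximation). At 200 per arm, non-inferiority power is 99.96% for broaching time. It is the same for OR time, because 3.75/7.5 = 1.25/2.5 = 0.5. Superiority power at 1 min is 99.1%.

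**2. Effect of adjustment on broaching time at the planned SD.**

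| R² | Residual SD (min) | Distance to limit (min) | Superiority power, 1 min | Superiority power, 0.5 min |
|---|---|---|---|---|
| 0 | 2.500 | 0.412 | 99.1% | 63.7% |
| 5% | 2.437 | 0.402 | 99.3% | 65.7% |
| 10% | 2.372 | 0.391 | 99.5% | 67.7% |
| 20% | 2.236 | 0.369 | 99.8% | 72.2% |
| 30% | 2.092 | 0.345 | 99.9% | 77.1% |

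Non-inferiority power cannot rise by more than 100% − 99.96% = 0.04 points. In sample-size terms, 5% to 30% corresponds to 400/0.95 = 421 up to 400/0.70 = 571 subjects in the unadjusted test.

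**3. Doubled SD (5 min).** Unadjusted non-inferiority power is 80.3%. The gain depends on what carries over:
- If R-squared stays at 5% to 30%, power is 82.0% to 91.0%.
- If the explained variance in min² stays fixed, it is 0.05 × 6.25 = 0.3125 up to 0.30 × 6.25 = 1.875 min², out of 25. That is 1.25% to 7.5%. The residual SD is √24.6875 = 4.969 down to √23.125 = 4.809, and power is 80.7% to 82.9%.

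**4. Does the stem-size argument carry to OR time?** Broaching variance is 2.5² = 6.25 min² against 7.5² = 56.25 min² for OR time, or 11%. Suppose stem size explains 30% of broaching variance and acts on OR time only through broaching, independently of the rest of the operation. It then explains 1.875/56.25 = 3.3% of OR-time variance. The limit distance falls from 1.24 to 1.6487 × 0.1 × √(56.25 − 1.875) = 1.22 min.

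**5. Cost in degrees of freedom.** With up to 20 sites and a few covariates, about 370 df remain. The critical value moves from 1.6487 to 1.6490, which is negligible.

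**The case against.** The strongest reply is that nothing changes under the plan's own assumptions. Study success rests on primary non-inferiority alone, its power is already 99.96%, and randomisation makes the t-test valid. Every material gain above needs an assumed R-squared, and the power gains also need a smaller true effect or a larger SD. This stands, and it is why the point is optional.

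A reader might infer that planned stem size is the dominant predictor and largely fixes the number of broaching steps. The documents do not support that. No section links planned size to broaching time or ranks it above other variables. SAP 8.4 also records starting and skipped sizes, so the number of steps is not set by planned size alone. Protocol 7.1 makes templating optional, so planned size may be blank or of uneven quality. Noise of that kind reduces the gain but does not bias a randomised comparison.

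A reader might also infer that stem size would sharpen the OR-time test. Step 4 shows that it would barely do so. Any gain there would have to come from sex, BMI or site, and the documents give no size for it.

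Finally, a model with patient covariates but no site would be incomplete. Allocation is blocked within site, and the Introduction of the Protocol asks each surgeon to use one stem system. Stem system, and possibly blank plans, may therefore track site. This stands, so site belongs in the model.

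**Conclusion.** The point holds as an optional refinement. Both time endpoints are tested without covariates that the trial already collects, and adjustment could make the limits somewhat tighter at almost no cost. It is not an error: the reading that the unadjusted t-test is invalid, or puts the primary conclusion at risk as planned, is not supported.

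The likely size is uncertain. For broaching time, the limit would be 2% to 16% closer to the estimate (0.402/0.412 and 0.345/0.412) if R-squared lies between 5% and 30%, a range that is assumed. The superiority test gains visibly only if the true benefit is well below 1 minute or the SD is larger than planned. Under a doubled SD, the gain in non-inferiority power could be as little as 0.4 points or as much as 10.7 points, depending on whether the covariates explain a fixed amount or a fixed share of the variance.

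**What to change.** Before database lock, amend SAP 8.7 and 8.8.1 and Protocol 10.5.1, 10.5.2, 10.9.3 and 10.9.4 as follows:

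- **Both endpoints:** a linear model with arm, site, sex and BMI.
- **Broaching time only:** add planned stem size within stem system, because Exhibit B shows Actis sizes 1 to 12 and Corail sizes 6 to 20 on different scales. Use a missing-value indicator where the plan is blank.
- **Decision rule:** compare the one-sided upper 95% limit of the arm coefficient with the unchanged margins of 1.25 and 3.75 min. Take the superiority test from the same broaching-time model.
- **Supportive analysis:** keep the two-sample t-test.
- **Exclude:** starting and ending broach size, which are recorded after randomisation and may be affected by the arm.

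The cost is wording in two documents and a slightly less simple primary analysis. No new data are needed. A sponsor that prefers to keep the t-test as primary could pre-specify the same model as supportive. The limits used for the decision would then be no tighter, but an adjusted estimate would be fixed in advance and not chosen post hoc in an open-label trial.

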3.5.4 Postoperative Withdrawal

A postoperative withdrawal is a Subject who has signed the Informed Consent Form and has been randomized, has received the standard of care study devices, and is later withdrawn from study participation (i.e. withdrawal of consent, revision, death, etc.). See **Table 3-3** below for more examples. All data obtained up to the date of withdrawal will be included in the clinical analysis.

Example	Actions	Follow-up
Subject withdraws	Document Subject's request for withdrawal from the study and Complete End of Study/Withdrawal CRF	Do not continue
consent		
Death	Complete Adverse Event CRF and Complete End of	Do not continue
	Study/Withdrawal CRF	
Revision	See Section 3.5.5 below for more information	Do not continue if the
		metal cup or stem has
		been revised.

Table 3-3: Postoperative Withdrawal Examples

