4.1 Primary Objective, Endpoint, and Associated Hypotheses

The primary endpoint is the mean femoral broaching in minutes collected intraoperatively. Femoral broach time should be collected intraoperatively in minutes and seconds and should begin at the time the box osteotome first enters the femoral canal and end with seating of the final broach trial within the femoral canal.

The primary objective of this study is to demonstrate that the mean femoral broaching time with KINCISE is non-inferior to the mean femoral broaching time with manual instruments when used in THA with Anterior Advantage.

If non-inferiority is successfully demonstrated then the study will be deemed successful, and a test for superiority for mean femoral broaching time will be conducted.

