10.9.3 Primary Endpoint

The primary endpoint analyses, described in section 10.5.1, will be performed on the Per Protocol Population set. The primary endpoint will be summarized as a continuous endpoint for both treatments. The difference in means $\mu_I - \mu_C$ will also be summarized as a continuous endpoint. Its 1-sided upper 95% confidence limit and the p-value for the test of non-inferiority with a margin of 1.25 based on a 2sample t-test will be produced. If non-inferiority is demonstrated, i.e. the p-value is < 0.05 then the test of superiority will proceed, and its p-value will be produced.

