Sticker sheets were created, one set for up to 30 sites, containing treatment assignments for 120 subjects using a fixed block size of 4 and a treatment allocation ratio of 1:1. On the face of each sticker is a character in the sequence A, B, C,, X, Y, Z, AA, AB, AC,AX, AY, AZ, BA, BB, BC, etc...., BX, BY, BZ, CA, etc...

The stickers should be removed sequentially to reveal the randomization code and treatment group ('Study (Kincise)' or 'Control (Mallet)') for each consecutive consented subject that meets eligibility criteria. Peeled sticker should be placed on the screening log to document that randomization was unbiased. The planned randomization group should then be documented in the applicable source document and on the Randomization eCRF (eCRF RDM) in the database.

The assigned treatment will remain secret to site personnel until subject is found to meet all eligibility criteria; No other blinding is implemented in this study.

4 Interval Windows

The study includes the following periods: Pre-op, Operative, Immediate post-op, 6 Week, 24 Week. Intervals related to each are shown in Table 3, below.

Visit	Minimum Day	Maximum Day	Midpoint Day
Pre-Op	-180	0	
Operative	0	0	0
Immediate post-op	0	Discharge	
6 week	14	60	37
24 week	61	200	130

 Table 3
 Interval Windows for Non-Radiographic Study Visits

Time point specific data collected to satisfy the primary and secondary efficacy-related objectives will be assessed for compliance with these intervals. Only data which can be attributed to the visit intervals in Table 3 will be used in the analysis of primary and secondary endpoints. This visit will be hereafter referred to as the Analysis Visit and the originally recorded visit as the Nominal Visit. If multiple measurements fall into the pre-operative window, or into the 'Immediate post-op' post-operative window, the result collected most proximate to surgery will be utilized. For the '6 week' and '24 week' visits, if multiple measurements fall into the window will be utilized for analysis.

5 Levels of Significance

The level of significance is 95%. Primary endpoint analyses, further described in section 8.7, and secondary endpoint analyses with hypotheses, further described in 8.8, will use 1-sided 95% confidence intervals and associated p-values. Data summaries of secondary endpoints without hypotheses and of exploratory endpoints will use 2-sided 95% confidence intervals and associated p-values.

6 Analysis Sets

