8.13 Sensitivity Analyses

No sensitivity analyses will be conducted.

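### Both broaching-time tests run only on the Per Protocol set, with no companion analysis of all randomised subjects by assigned arm

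*SAP*

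**What the plan says.** Both documents put the primary tests on one set. Protocol 10.9.3: "The primary endpoint analyses, described in section 10.5.1, will be performed on the Per Protocol Population set". SAP 8.7: "The primary endpoint analysis and all associated hypotheses will be conducted on the Per Protocol Analysis Set", which takes in the superiority test. SAP 8.13 adds: "No sensitivity analyses will be conducted".

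Three sets are defined (Protocol Table 10-1, SAP section 6): Enrolled, Safety (grouped by actual treatment) and Per Protocol. The SAP limits Per Protocol to subjects "who successfully received the planned treatment, who met all inclusion/exclusion criteria, who were seen at least once at a post-operative visit" and free of "protocol deviations which were prospectively determined to potentially have influence on the scientific validity of the data". Eligibility criteria are the only example given. SAP 8.2 also counts major violations of other kinds, without defining them.

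The broaching clock stops inside the operation; under Protocol 4.1 it must "end with seating of the final broach trial within the femoral canal". The arm is concealed until eligibility is confirmed, and after that "No other blinding is implemented in this study" (SAP section 3). For subjects withdrawn after surgery, Protocol 3.5.4 says: "All data obtained up to the date of withdrawal will be included in the clinical analysis".

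SAP 8.4, with the conventions of 8.1, plans n, mean and SD of broaching time by treatment on the Safety set as well as on Per Protocol.

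Protocol 10.2 decides treatment received by the broaching instrument alone. SAP section 2 decides it by broaching, stem impaction or both. SAP Table 10.1, which lists substantive changes from the protocol, has no entry for this.

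**The concern.** Randomisation protects the comparison of everyone randomised. Per Protocol keeps that protection only if exclusions are unrelated to broaching time. Here the endpoint is complete before several exclusion conditions are settled, the operating team knows the arm, and successful receipt of the planned treatment is not defined. A recorded time can therefore leave the analysis because of how the operation went or what followed it. Intraoperative withdrawals are replaced (Protocol 3.5.3), so the set can reach its target size without them.

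If exclusions differ by arm and relate to duration, the estimated difference moves, and no planned test or confidence limit would show by how much. This matters most for superiority, where a per-protocol result has no full-set analysis behind it. For non-inferiority, Per Protocol is a sensible set, and what is missing is the second view.

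**Working it through.** **1. The plan's own figures.** Inputs from Protocol 10.8 and SAP section 7: SD 2.5 min, margin 1.25 min, one-sided 5%, 200 per group.
- N for 95% power: 2 × (2.5/1.25)² × (1.645 + 1.645)² = 86.6, so 87 by the normal formula. The noncentral t gives 88, the stated figure (95.1%).
- SE at 200 per group: 2.5 × √(2/200) = 0.25.
- Non-inferiority power: Φ(1.25/0.25 − 1.645) = 99.96%.
- Superiority power at 1 min: Φ(1/0.25 − 1.645) = 99.1%.

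All reproduce. The sample size is not in question.

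**2. How a recorded time can leave Per Protocol.**
- *Planned treatment not successfully received*: not defined.
- *Deviation*: must be determined prospectively, but no list is given beyond eligibility.
- *No post-operative visit*: probably removes few. The synopsis schedule has subjects seen at discharge, and SAP Table 3 lists an immediate post-op row. The Study Visit form is not marked for that column in Protocol Table 0-1, so this is not conclusive. The condition sits uneasily with Protocol 3.5.4.
- *Intraoperative withdrawal*: the time may not be on file. Protocol 3.5.2 asks for preoperative data, the End of Study form and any adverse event form. Protocol section 11 asks for operative details on all Subjects.

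**3. Illustrative size.** The documents give no exclusion rates or delays, so those below are assumptions. Let a fraction fK of the KINCISE arm and fC of control be dropped, with those cases dK and dC minutes longer than the rest of their arm. The target is the difference by assigned arm among subjects with broaching started.
- Shift towards KINCISE = fK·dK − fC·dC
- SE = 2.5 × √(1/(200(1−fK)) + 1/(200(1−fC)))
- Error = Φ(shift/SE − 1.645), the same at a true difference of 0 (superiority) and of 1.25 (non-inferiority)

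| Dropped cases | Shift / SE | Per Protocol error |
|---|---|---|
| 2% of KINCISE, 5 min longer | 0.100 / 0.2513 | 10.6% |
| Same, plus 1% of control, 5 min longer | 0.050 / 0.2519 | 7.4% |
| 2% of both arms, 5 min longer | 0 | 5.0% |
| 2% of control only, 5 min longer | −0.100 / 0.2513 | 2.1% |
| 2% of KINCISE, 5 min shorter | −0.100 / 0.2513 | 2.1% |

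The first row falls to 7.4% if either the delay or the fraction is halved, and to 6.1% if both are. In 200,000 simulated trials per row, the assigned-arm t-test had error between 4.85% and 5.15%.

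**4. Power of a full-set analysis.** Keep the 2% of KINCISE cases that run 5 min longer. SE = √((6.25 + 0.02 × 0.98 × 25)/200 + 6.25/200) = 0.2548.
- Non-inferiority, other cases equal: Φ((1.25 − 0.10)/0.2548 − 1.645) = 99.8%.
- Superiority, other cases 1 min faster with KINCISE: Φ((1.00 − 0.10)/0.2548 − 1.645) = 97.0%.

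**5. Why Per Protocol stays for non-inferiority.** Crossover dilutes an assigned-arm contrast. With a true as-treated difference of 1.25 min and 5%, 10% or 20% of KINCISE cases broached by mallet, the assigned-arm test passes Φ((1.25 − 1.25(1−c))/0.25 − 1.645) = 8%, 13% or 26% of the time. The two sets complement each other.

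**6. Treatment received.** Two kinds of case are classified differently:
- KINCISE-assigned, broached by mallet, stem impacted with KINCISE: mallet under Protocol 10.2, KINCISE under SAP section 2.
- Mallet-assigned, KINCISE used only for the stem: mallet under Protocol 10.2, KINCISE under SAP section 2.

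Both depart from Protocol 3.4. Neither document says whether such a departure excludes from Per Protocol.

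**The case against.** The best defence is SAP 8.4. The Safety set keeps everyone in whom treatment was attempted, and n, mean and SD per group are all that a two-sample t-test needs. A reader could approximate the contrast from planned output, so it would be wrong to infer that excluded times vanish from the report. That stands as partial mitigation. Safety still groups by treatment received under the disputed rule, carries no planned test or confidence limit, and may lack times for intraoperative withdrawals.

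Other points that stand:
- Inside Per Protocol, assigned and received arm should largely coincide, so the gap concerns the randomised subjects left out and not mislabelled arms.
- Success rests on non-inferiority alone. Superiority is supplemental, and SAP 8.8 lets the secondary tests proceed whatever its result.
- Counts by treatment (SAP 8.2) and deviation listings (SAP 8.6) would make an imbalance visible, though not its effect on the limit or p-value.

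A reader might also infer that the exclusions favour KINCISE. The written rules do not support that. Under Protocol 3.4, extra mallet use in a KINCISE case is not a deviation if KINCISE did the broaching, and the SAP rule keeps a converted case in KINCISE. Control must use the mallet at every step, so control has more ways to deviate. Nor do the documents show that operative data go uncollected for intraoperative withdrawals; Protocol 3.5.2 and section 11 disagree.

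**Conclusion.** The point holds as a gap in the plan that should be fixed. Both tests use Per Protocol only, no analysis of all randomised subjects by assigned arm is planned, and sensitivity analyses are ruled out. The gap matters most for superiority. The stronger reading, that a Per Protocol non-inferiority test is invalid or that the true error is 11%, is not supported: Per Protocol is not wrong in itself for non-inferiority, and the 2% to 11% range rests wholly on assumed exclusions of 2% of cases differing by 5 minutes. The direction and size of any bias cannot be derived from the documents, and with few or balanced exclusions there would be little or none.

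The mismatch in treatment received is a separate, verifiable inconsistency. Its effect on the primary test is limited if departures from Protocol 3.4 lead to exclusion, which the documents leave open.

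**What to change.** 1. Define a Full Analysis Set: all randomised subjects with broaching started and a recorded time, analysed by assigned arm. Test superiority on it. Report the same non-inferiority confidence limit on it beside Per Protocol, and address any disagreement in the conclusion. Report by arm how many randomised subjects fall outside it, because it still conditions on broaching having started and a time being on file.
2. Remove the post-operative-visit condition for broaching time and skin-to-skin time.
3. Reconcile Protocol 10.2 and SAP section 2 to one treatment-received rule and list the change in SAP Table 10.1. Define successful receipt of planned treatment, and state before data review which departures from Protocol 3.4 exclude from Per Protocol.
4. Reconcile Protocol 3.5.2 with section 11 so that the existing Operative Details eCRF is submitted for intraoperative withdrawals in whom broaching was started.

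The cost is wording in both documents, one more run of the same t-test and an existing form for some subjects. No extra patients are needed. The loss of power is small, as step 4 of the working shows.
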